Official Study Title: Managing Diabetes to Gain Opportunities for a More Active Life (My Diabetes GOAL)

Unique Protocol ID: IRB18-0425

Date of approval by the University of Chicago Human Subjects review board: 7/9/2018

Detailed Protocol

1. Background:

Health systems are striving to optimize chronic disease management, improve health outcomes, enhance patient safety, and control health care costs. An important high risk population in health care systems is older adults living with diabetes. Patients over 65 years of age represent over 40 percent of patients living with diabetes.¹ In the coming decades, this population is expected to grow exponentially.² This population suffers from high rates of cardiovascular and microvascular complications as well as hypoglycemia, a consequence of treatment.³ Despite these poor outcomes, optimal approaches to providing diabetes care for this population have not been adequately established. Clinical trials of intensive glycemic control have demonstrated long-term benefits but short-term harms.⁴⁻⁶ In light of the mixed trial results, multiple organizations have called for the personalization of risk factor goals, medication management, and self-care plans among older patients.^{7,8} For instance, the American Geriatrics Society (AGS)⁹ and the American Diabetes Association (ADA)¹⁰ have published recommendations urging individualized glycemic (hemoglobin A1C (A1C) <7.5% vs. <8.0% vs. <8.5%) and blood pressure (BP) control targets (<140/80 vs. <150/90 mmHg) and statin use for three strata of older patients (healthy, complex, very complex). The guidelines also acknowledged the importance of overcoming barriers to self-care management in older patients. Despite the release of these guidelines, studies of multiple national datasets have demonstrated that care of older patients is not currently being personalized based on health status.^{11,12} The failure to personalize care may lead to both overtreatment of the sickest patients, as well as undertreatment of healthy patients. The barriers to providing personalized care for older people may be due to a lack of care support interventions that can be integrated into busy practices. Many clinical organizations have diabetes quality improvement systems in place, but these efforts typically do not promote individualized goals and do not have a geriatric orientation.

2. Purpose or Hypothesis:

The purpose of this novel patient-facing disease management intervention, **My Diabetes GOAL**, is to develop and test a system embedded within the electronic medical record to engage patients in personalized goal setting and chronic disease management by: 1) establishing personalized goals of care based on comorbidities and preferences, 2) tracking diabetes measures against personalized goals, and 3) selecting the route and intensity of care management to help patients achieve their goals (e.g., telephonic care management, in-person care management, and self-care resources). This application can be used to individualize care, increase engagement with patient portals, and improve patient self-efficacy, as they take a more active role in their care.

3. Description of Protocol Methodology:

We will conduct a 6-month randomized controlled trial comparing My Diabetes GOAL vs. usual care within University of Chicago clinics (endocrinology, primary care group, and geriatrics). After agreeing to participate, patients will be randomly assigned to each arm, for a total of 50 patients per arm. Patients that are enrolled in the intervention arm will receive an email message via MyChart to complete the initial questionnaire. If there is an initial non-response, we will try three additional times over a one month period. Completion of the questionnaire will be required prior to initiating risk factor tracking and opening the portal to requests for care management support. Patients enrolled in the usual care will receive the My Diabetes GOAL survey with a 6 months delayed start.

Prior to receiving the survey, they will be able to continue to receive routine diabetes care and education provided by diabetes educators and clinical staff. Upon completion the study, all patients will receive a post-survey via MyChart. Electronic Health records will be a critical source of data on key processes of care that are affected by My Diabetes GOAL including goal setting measures (documenting personalized goals of diabetes care, proportion following ADA recommendations, proportion choosing alternative goals) as well as referrals to care management and frequency of phone contacts. The EHR will also be the primary source of data for risk factor levels (glycosylated hemoglobin, blood pressure, cholesterol levels), medications, and health care utilization (outpatient visits, care management services, ER visits, and hospitalizations). These data are continually collected as a part of routine care.

4. Duration:

The initial MyChart survey should not take more than 10 minutes to complete. The post-survey should not take more than 5 minutes to complete. Enrollment in services or receipt of telephonic care management is up to the patient, and dependent on their responses to the survey questions. After 6 months, we will terminate telephonic care management follow-up phone calls.

5. Exact Location:

The surveys will be conducted online.

6. Special precautions: n/a

7. Experimental controls:

50 control patients will receive a delayed intervention so we can compare usual care versus the intervention arm, but still distribute the survey and potential telephonic care management to the control arm at a later date. Patients will be the units of randomization. We will enroll patients over 65 years of age with active MyChart accounts, diagnosis of type 2 diabetes, and outpatient clinic visit in the prior year. Because of the general purpose of the intervention, we will not exclude patients with comorbid illnesses or functional impairments. We plan to enroll 100 patients. We will determine trial arm assignment through a random number generator.

8. Outcome measures:

The primary endpoint is documentation of a personalized goal for diabetes care (e.g., A1C target) (yes or no) in 6 months. Secondary endpoints include patient engagement with MyChart, patient selection of personalized goals, patients' ability to reach their personal treatment goals. We will also collect data on hypoglycemia, psychosocial measures, and health care utilization. It is also possible that changes in patient reported outcomes and utilization will occur earlier than expected through mechanisms that are separate from changes in drug prescribing and risk factor control.

The **documentation measures** (utilization of MyChart, documenting personalized goals of diabetes care, proportion following ADA recommendations, proportion choosing a goal different from the ADA recommendations) will be assessed by comparing results from the EHR at baseline (6 month lookback) and at 6 months of the trial. For **short-term clinical outcomes**, we will evaluate changes

in the proportion of patients with out-of-range A1Cs (A1C>9.0%, A1C<6.5% taking insulin/sulfonylureas) and blood pressures (BP>150/90, BP<120/65). We will also assess changes in the proportion of patients taking statins and specific glucose lowering agents. These analyses will be done for the overall population along with comparisons of drug use by the ADA risk strata. To evaluate **health care utilization**, we will again utilize the EHR to determine the frequency of referrals to telephone care management, the source of referrals (population management, physician), the patient predictors of referrals, and to characterize frequency and content of telephonic management.

9. Statistical analysis:

For the primary endpoint analysis, we will use the Fisher's exact test, and the logistic regression model to compare the two groups. We will also use both the generalized linear mixed model (GLMM) and the generalized estimating equation (GEE) to model % documentation over time (at baseline and 6 months) and test the effects of treatment, time, and interaction between treatment and time. We will first fit unadjusted model and then adjust for potential risk factors such as age, gender, race, and its baseline outcome. Within-subject correlation will be taken into account.

For the analyses of secondary endpoints, we will conduct between-cohort analyses for those outcomes which can be obtained for both groups, mainly through EHR, and conduct within-cohort analyses for those outcomes which can be collected only in the intervention group.

For between-cohort analyses, for the repeated-measured continuous outcomes such as A1c and BP, we will use a linear mixed model (LMM) to model the outcome over time and test the effects of treatment, time, and treatment-by-time interaction. For the repeated-measured binary outcome such as utilization of MyChart and following ADA recommendations, the same statistical methods as for the primary endpoint will be applied. A Wilcoxon's rank-sum test, and the bootstrapping method will be used to compare frequencies of each type of health care utilization (primary care, emergency room, and hospital visits) for prior 6 months, at baseline and 6 months, and their changed frequencies at 6 months from baseline, respectively. A GEE will also be used to model the frequencies of health care utilization over time.

For within-cohort analyses, i.e., within the intervention group, for the continuous outcome (which will be measured once during the study) such as patient engagement with MyChart, a multiple linear regression will be performed to test the time trend, i.e., conduct self-comparison (post versus before). For the repeated measured binary outcome such as patients' awareness of their A1c goal, both GLMM and GEE will be used to test the time trend. For the binary outcome (which will be measured once during the study) such as achieving their A1c goal at 6 months, the logistic regression model will be used to test the time trend.

We will repeat the analysis plan above, if necessary, at 12 months for the available outcomes from EHR for sustainability check between the groups and/or within cohort.

Power and sample size justification: The primary outcome is documenting personalized goals of diabetes care in 6 months. We expect that at baseline, in both groups, there would have <5% patients whose charts have been documented their personalized goals. We presume that the intervention group will have more than 50%. Using the Fisher's exact test, a total sample size of 44 subjects (22 per group) is needed to obtain at least 90% power to detect the difference between the two groups at a two-sided significance of 5%. With a total sample size of 100, the power will be >0.99.

10. Potential risks and benefits to subjects: The risks include loss of confidentiality. The potential benefits include an improvement in their health through additional screening for risks associated with their chronic disease, improved communication with their physician, referrals to beneficial resources that they may not be aware of, which could improve patient outcomes.
11. Monitoring of safety of subjects: The subjects will be monitored via the survey responses and screened for any potential risks for harm. If the diabetes care manager conducts telephonic care management with patients, they will also be monitored for safety by a registered nurse. There is no DSMB for the study as there are no unanticipated risks to the subjects.
12. Payment to subjects: Subjects will not be paid for this study.
13. Procedures to obtain and record informed consent: We will call patients and ask them if they would be interested in participating in the study. If they are interested, we will either email, fax, or mail a copy of the informed consent document. Once received, we will review the document together and if the patient consents to participate, they will sign the document and either fax or email a scanned copy of the consent back to the research office, or mail it back to the study research office. Once the signed consent form is received, the patient will receive an email via MyChart inviting them to participate in a survey.
14. Procedures which will be used to maintain confidentiality: All information obtained for analysis will de-identified. All informed consent forms will be kept in a locked cabinet. All data will be stored on secure network drives and any written information will be kept in locked cabinets.
15. Bibliography: Please refer to the end of the document.
16. Description of recruiting methods: Subjects were identified via an ACRES report. There will be no advertisement for this study.
17. Description of how the subject's primary physician will be notified of and, as appropriate, involved in the proposed research: Subjects' primary care physician will be sent an email asked to assent for their patient to participate in the study prior to the study staff reaching out to individual patients.

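### Patient-reported measures have no pre-randomisation baseline in either arm, and A1c-goal awareness is tested only as a one-arm trend; a between-arm month-6 comparison with a short baseline is a cheap improvement

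*Combined protocol and SAP*

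**What the plan says.** Section 3 (Description of Protocol Methodology) sets the order of events. Assignment comes straight after agreement: "After agreeing to participate, patients will be randomly assigned to each arm, for a total of 50 patients per arm". The first survey then goes to one arm: "Patients that are enrolled in the intervention arm will receive an email message via MyChart to complete the initial questionnaire". Non-responders are chased: "If there is an initial non-response, we will try three additional times over a one month period". Completing the questionnaire is what starts risk-factor tracking and opens requests for care management. For the other arm: "Patients enrolled in the usual care will receive the My Diabetes GOAL survey with a 6 months delayed start". Section 7 gives the reason: the survey is withheld from controls as part of the delayed intervention. The only other survey in section 3 is the closing one: "Upon completion the study, all patients will receive a post-survey via MyChart".

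Section 8 (Outcome measures) says that psychosocial measures will be collected, without naming an instrument or a schedule, and remarks: "It is also possible that changes in patient reported outcomes and utilization will occur earlier than expected". Section 2 (Purpose) says the application can be used to "increase engagement with patient portals, and improve patient self-efficacy". Documentation measures taken from the EHR do have a baseline, by a 6-month lookback.

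Section 9 (Statistical analysis) compares the arms on outcomes obtainable in both, mainly through the EHR, and analyses within the intervention group those that can be collected only there. Its example of a repeated binary outcome in the second class is awareness of the A1c goal, tested for a time trend by GLMM and GEE.

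Section 13 (informed consent) adds a sentence that names no arm: "Once the signed consent form is received, the patient will receive an email via MyChart inviting them to participate in a survey".

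**The concern.** A lookback supplies baseline values for laboratory results, prescriptions and visits. It cannot recover what a patient knew or felt. For such measures the schedule gives no value before assignment in either arm. The nearest thing to a starting value exists only for intervention patients who completed the questionnaire. It may come as late as a month after the first invitation, and it is recorded on the instrument that begins the intervention.

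A before-after trend in that group mixes any effect of the tool with the passage of time, regression to the mean and the self-selection of completers. A randomised trial would then be giving up its control group for an outcome it could compare between arms. At stake are the interpretation of the patient-reported results, the precision of the valid comparison, and the means to examine or adjust for non-response to the post-survey.

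**Working it through.** **Survey schedule, from sections 3 and 7**

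| Time | Intervention arm | Usual-care arm |
|---|---|---|
| Before assignment | none described | none described |
| After assignment | initial questionnaire, up to three further attempts over one month | none described |
| Month 6 / study completion | post-survey | post-survey and delayed My Diabetes GOAL survey, order not stated |

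Two things follow. No patient-reported change from a pre-randomisation value can be formed in either arm. Post-survey values, however, are planned for both arms, so month-6 levels can be compared as randomised, provided controls answer before the delayed survey reaches them. The timing in section 3 (completion of the study) does not secure that order.

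**The plan's own figure.** Section 9 gives 22 per group for at least 90% power with Fisher's exact test, and power above 0.99 at a total of 100. Exact enumeration at 5% against 50%, two-sided 5%, gives 0.927 at 22 per group and 0.9998 at 50 per group. The smallest size reaching 90% is 21 per group (0.911), total 42 against 44, which is immaterial. The calculation reproduces and is untouched by this point, because goal documentation comes from the EHR in both arms.

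**Precision of the month-6 comparison.** The documents give no SD, no response rate and no correlation r between baseline and follow-up. Assumptions: a continuous score; two-sided 5%; 80% power; normal approximation; r = 0.3, 0.5 or 0.7; either all 50 per arm responding or 70% of them (35 per arm); a baseline for every respondent.

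- Without a baseline: detectable difference = (1.96 + 0.8416) × √(2/n), in SD units.
- With a baseline in an analysis of covariance: the same × √(1 − r²).
- n = 50: 2.8016 × √(2/50) = 2.8016 × 0.2000 = 0.560.
- n = 35: 2.8016 × √(2/35) = 2.8016 × 0.2390 = 0.670.
- √(1 − r²) = 0.954, 0.866 and 0.714 for r = 0.3, 0.5 and 0.7.

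| Respondents per arm | No baseline | r = 0.3 | r = 0.5 | r = 0.7 |
|---|---|---|---|---|
| 50 | 0.56 SD | 0.53 SD | 0.49 SD | 0.40 SD |
| 35 | 0.67 SD | 0.64 SD | 0.58 SD | 0.48 SD |

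The equivalent gain in respondents is 1/(1 − r²) − 1: 10%, 33% and 96%. For a true difference of 0.5 SD with 50 per arm, power is 0.705 without a baseline and 0.746, 0.823 or 0.938 with one.

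The gain is smaller if some respondents skip the baseline. A simple change score would be the wrong use of it: its factor is √(2(1 − r)), which at r = 0.3 raises the detectable difference at n = 50 from 0.560 to 0.663 SD.

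**The case against.** The strongest reply is that randomisation makes a baseline unnecessary for validity. The month-6 difference between arms estimates the same effect as a difference in changes, and the post-survey goes to all patients. That stands. A reader might infer from the schedule that patient-reported outcomes cannot be compared between arms at all; the documents do not support this.

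A reader might also infer that section 9 sends all psychosocial measures to the one-arm analysis. It does not mention them. Its within-cohort rule covers only outcomes that can be collected in the intervention group alone, and anything on the post-survey can be collected in both. The criticism of the analysis therefore attaches to the example that section 9 gives, awareness of the A1c goal. Reading that as patient-reported is an inference, though a natural one.

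The targets are also peripheral. Psychosocial measures and goal awareness are not among the primary or listed secondary endpoints. Self-efficacy appears only in the Purpose, with no instrument, so its absence from the outcomes is not evidence of a failed endpoint. The section 8 remark on changes in patient-reported outcomes is about timing and mechanism and commits to no analysis.

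Section 13 can be read as inviting every patient to a survey on receipt of consent. If so, controls would have an early value. Section 3 is the more specific text and section 7 supports it, so the delayed reading is likelier, but the two have to be reconciled.

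Finally, the gain is wholly assumed and at r = 0.3 is slight. That also stands.

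**Conclusion.** This is a cheap improvement and does not undermine the trial. As scheduled in section 3, patient-reported measures lack a pre-randomisation baseline in both arms, and section 9 tests at least one such outcome without the control group. Correcting the analysis costs almost nothing and removes a real source of bias. Adding a baseline buys precision: with 50 per arm the detectable difference falls from 0.56 SD to between 0.53 and 0.40 SD, and with 35 per arm from 0.67 SD to between 0.64 and 0.48 SD. These figures rest on assumed r from 0.3 to 0.7, assumed response and complete baselines. The primary endpoint, A1C, blood pressure, medications and utilisation come from the EHR and are unaffected. The stronger conclusion, that the patient-reported results could not be compared between arms, goes beyond the documents.

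**What to change.** 1. **Section 9:** compare post-survey items (psychosocial measures, A1c-goal awareness) between the randomised arms at month 6. Report the intervention-only change as descriptive.
2. **Section 3:** state that controls complete the post-survey at month 6, before they receive the delayed My Diabetes GOAL survey. Without this, the comparison in step 1 could be contaminated.
3. **Baseline:** after consent and before assignment, send every patient a short neutral set of the same psychosocial items through MyChart. Include no goal questions, and do not make completion a condition of randomisation. Adjust the month-6 comparison of these items for it, and state how a missing baseline is handled so that no randomised respondent is dropped. Goal awareness would stay an unadjusted month-6 comparison, because asking about goals beforehand could prompt controls. Include self-efficacy only if the sponsor intends to measure it, and then name the instrument.
4. **Section 13:** reconcile the survey invitation on receipt of consent, which names no arm, with the delayed start in section 3.

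Steps 1, 2 and 4 are changes of text. Step 3 costs a few minutes per patient on a platform that all participants already use. The changes need an IRB amendment. There are two downsides. Being asked may alter controls' later answers. The baseline also adds a little MyChart activity in both arms, which should be excluded from the MyChart utilisation outcome. Step 3 has to be in place before patients are assigned, since this baseline cannot be collected afterwards.

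### Patients come from three clinic types, but the plan describes allocation only as a random number generator and names no clinic term, so nothing stated secures clinic balance; the effect is modest and confined to secondary outcomes and allocation predictability

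*Combined protocol and SAP*

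**What the plan says.** Section 3 places the trial "within University of Chicago clinics (endocrinology, primary care group, and geriatrics") and says that "patients will be randomly assigned to each arm, for a total of 50 patients per arm". Section 7 gives matching totals ("50 control patients will receive a delayed intervention"; "We plan to enroll 100 patients"), sets the unit ("Patients will be the units of randomization") and describes the method in one sentence: "We will determine trial arm assignment through a random number generator". No blocking, stratification, list type, list holder or release step is described. Section 3 places assignment after the patient has agreed to take part. Section 13 has the study team telephone patients and go through the consent form with them.

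Section 9, on the primary endpoint, says: "We will first fit unadjusted model and then adjust for potential risk factors such as age, gender, race, and its baseline outcome". Binary secondary outcomes use the same methods. The linear mixed model (LMM) paragraph for A1C and BP tests treatment, time and their interaction and names no covariates. Utilization is compared by a rank-sum test and bootstrap at baseline, at 6 months and as change, and also by GEE. Clinic appears nowhere in section 9.

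**The concern.** Clinic type is known before randomization and costs nothing to record. Endocrinology, primary care and geriatrics plausibly differ in how often goals are written down, in A1C and treatment, and in visit frequency, although the documents give no data by clinic. These are all trial outcomes. When such a factor is controlled neither in the allocation nor in the model, one arm can by chance hold more patients of one clinic type. The secondary comparisons are then noisier and harder to interpret.

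The second issue is the allocation process. The protocol states a target of 50 per arm but no mechanism. Some ways of reaching an exact 50, such as closing an arm once it is full, make the last assignments known in advance. The protocol does not say that the people making recruitment calls are kept apart from the list.

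**Working it through.** **Inputs.** From the documents: 100 patients, 50 per arm, three clinic types (sections 3 and 7); documentation below 5% at baseline in both groups and above 50% with the intervention, two-sided 5%, Fisher's exact test, 22 per group for at least 90% power, and power above 0.99 at 100 patients (section 9). I used 5% and 50%, with the control rate unchanged at 6 months. Assumed, because not given: the clinic shares and any difference between clinics.

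**1. The plan's own figure.** Power = Σₓ Σᵧ Bin(x; n_C, 0.05) · Bin(y; n_T, 0.50) · 1[Fisher p ≤ 0.05].
- 21 per arm: 0.911. 22 per arm: 0.927. The stated 44 in total is confirmed as sufficient.
- 50 per arm: 0.9998. The stated figure of above 0.99 is confirmed.

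**2. Arm sizes, if each patient were assigned independently.** With X ~ Bin(100, 0.5):
- P(X = 50) = 0.080.
- P(40:60 or worse) = 0.057.
- Central 95% range for one arm: 40 to 60.

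These hold only for independent assignment. A generator that shuffles a fixed list of 50 and 50 gives exactly 50:50.

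**3. Effect of arm sizes on the primary test** (control:intervention). Power is 0.9998 at 40:60, 0.9997 at 60:40, 0.9997 at 35:65, 0.9995 at 65:35, 0.9992 at 30:70 and 0.9989 at 70:30.

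**4. Clinic balance.** Largest between-arm difference in any clinic's share, in percentage points (100,000 draws per row):

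| Assumed patients per clinic | Independent: median / 95th pct | Fixed 50:50: median / 95th pct |
|---|---|---|
| 34/33/33 | 10.7 / 22.1 | 10 / 22 |
| 20/60/20 | 9.6 / 20.8 | 8 / 20 |
| 15/70/15 | 8.8 / 18.8 | 8 / 20 |
| 10/80/10 | 7.4 / 16.2 | 8 / 16 |

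For a single clinic of 20 patients, a 13:7 or worse split has probability 0.263 under independent assignment and 0.211 with 50 per arm fixed; for 14:6 or worse the figures are 0.115 and 0.078. Fixing the arm sizes therefore does not balance the clinics.

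**5. Effect of clinic imbalance on the primary test.** Take a 20-point imbalance and a clinic documentation rate of 20% or 50% against 5% elsewhere. The arm difference shifts by 0.20 × (0.20 − 0.05) = 0.03 or 0.20 × (0.50 − 0.05) = 0.09. Reducing the 45-point difference by these amounts leaves power at 0.999 and 0.994. Type I error of Fisher's test ignoring clinic (independent assignment, shares 20/60/20, 20,000 trials each) was 0.020 with 5% in every clinic, 0.030 with 20/2/20% and 0.040 with 50/10/50%.

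**6. Effect on A1C and BP.** Let d be the between-arm difference in one clinic's share and δ the amount by which that clinic's mean 6-month change differs from the others. The arm difference in change shifts by d × δ. A stable difference in level has δ = 0 and cancels from the treatment-by-time term. Only differing changes matter there, and from step 4 the shift would typically be about 7% to 11% of δ and, at the 95th percentile, 16% to 22% of it. The documents give nothing from which to set δ.

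**The case against.** A reader might infer that assignment is unstratified and that 50 per arm is left to chance. The documents do not support this. They are silent on method, and a random number generator can permute a fixed 50/50 list, so the 8% chance of an exact split applies only under independent assignment.

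A reader might also infer that the adjusted models could not correct a clinic imbalance. That goes too far. The covariate list is introduced as examples, so clinic is unnamed rather than excluded, and the baseline outcome, which is listed, absorbs part of any clinic difference already present at baseline. For A1C and BP a stable clinic difference drops out of the treatment-by-time test.

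Chance imbalance is not bias in a randomized comparison, since the confidence interval already allows for it. Closing an arm at 50 is a hypothetical with no text behind it, and the consent calls in section 13 do not show that callers hold the assignments. No secondary effect size is stated, so the precision to be gained cannot be quantified.

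The remedy has limits too. Stratified blocks do not guarantee 50:50: blocks of 4 in three clinics allow an imbalance of 2 per clinic, 6 overall, or 47:53. A patient may attend more than one clinic. With 5% of 50 controls, about 0.05 × 50 = 2.5 control events are expected, too few to support extra terms comfortably.

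All of this stands, and it limits the point to a modest improvement. It does not supply what is missing: the restriction method, the release step and the role of clinic in the analysis are unstated, and clinic balance is not secured even if the arms are fixed at 50.

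**Conclusion.** The point holds as a low-cost improvement and not as a flaw that threatens the main result. For the primary endpoint the effect is negligible on the plan's own rates: power was at least 0.994 in every scenario checked, and simulated type I error was at most 0.040.

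The remaining exposure lies in the secondary outcomes, for which the plan gives no power: A1C and BP, drug use, and utilization. For the treatment-by-time tests it arises only if clinics differ in their 6-month change. A stable difference in level would still affect the unadjusted comparison of utilization at 6 months. The 7-to-11-point median and 16-to-22-point 95th percentile rest on assumed clinic shares from 34/33/33 to 10/80/10. The benefit for allocation is that assignments become harder to foresee; nothing in the documents shows that they are foreseeable now.

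**What to change.** **Section 7.** State that a 1:1 list is generated before recruitment in permuted blocks of varying size, stratified by recruiting clinic. Define that as the clinic through which the patient was identified, fixed before assignment, so that a patient seen in two clinics has one stratum. Release each assignment only after signed consent is logged, from someone who does not make recruitment calls. Describe the arms as approximately 50 each.

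**Section 9.**
- Add clinic as a covariate to the LMMs for A1C and BP and to the models for the secondary binary and utilization outcomes. Where the test is treatment by time, include clinic by time as well. A clinic main effect adjusts the level, and with complete data at two time points it leaves the difference in change unaltered.
- Keep Fisher's exact test for the primary endpoint.
- For the sparse documentation models, prespecify any pooling of clinics by clinic size rather than by event counts, or use a penalized likelihood.
- If clinic is left out, say why.

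**Cost.** A short program, a few sentences, two degrees of freedom per model for clinic, and two more where clinic by time is included. If recruitment has begun, the clinic terms can still be specified before analysis.
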